8.0 CRITERIA FOR RESPONSE

8.1 Hematologic response:

Complete hematologic response is defined as a white blood cell count $<10 \times 10^{9}$ /l, a platelet count $<450 \times 10^{9}$ /l, no blasts in the peripheral blood and disappearance of all signs and symptoms related to leukemia, including palpable splenomegaly.

8.2 Cytogenetic response:

Cytogenetic assessments are based on at least 20 metaphases or fluorescence in situ hybridization with at least 200 cells on peripheral blood or bone marrow Cytogenetic response can be categorized as:

- Complete: 0% Ph+ metaphases;
- Partial cytogenetic response: 1%-35%;
- Major cytogenetic response, 0%-35%;
- Minor cytogenetic response, 36%-65%;
- Minimal cytogenetic response, 66%-95%;
- No cytogenetic response, > 95%.

8.3 Molecular response:

Molecular assessments are based on quantitative reverse transcriptase polymerase chain reaction for Bcr-Abl in peripheral blood. Molecular response is categorized as MMR (Bcr-

Abl/Abl ratio of < or =0.1% in the International Scale), MR4 (Bcr-Abl/Abl < or =0.01%), and MR4.5 (BCR-ABL/ABL < or =0.0032%).

To convert M.D. Anderson BCR-ABL results to the international scale, multiply result by 0.35.

8.4 Survival:

- Overall survival: Overall survival is calculated from the start date of therapy to the date of death or last follow-up.
- Failure-free survival: Failure-free survival is measured from the start of study drug to the
 earliest date of the following: an event as defined for event-free survival, transformation
 to AP or BP, intolerance, treatment discontinuation for any reason (as assessed by
 investigator), or death from any cause while on bosutinib therapy.
- Event-free survival (EFS): EFS is defined as the time from treatment start until any of the following events that occur during study treatment: loss of complete hematologic response (CHR); loss of major cytogenetic response (MCyR); progression to AP/BP; death due to any cause.
- Transformation-free survival: Transformation-free survival is defined as the time from treatment initiation until either progression to AP/BP or death from any cause.

9.0 EVALUATION OF TOXICITY

Toxicities will be graded in the research nurse/PI dictations in the medical record, according to the NCI Expanded Common Toxicity Criteria version 4.03 or later.

10.0 CRITERIA FOR REMOVAL FROM THE STUDY

Criteria for removal from study include, but are not restricted to, the following:

- 1. Clinically significant progressive disease, defined as accelerated phase (except clonal evolution as the only criterion for accelerated phase) or blast phase, loss of complete
- 2. Recurrent non-compliance by the patient with protocol requirements.
- 3. Patient's request to be removed from the study.
- 4. Unacceptable toxicity.

5. Failure to respond at 3, 6, 12 months according to European LeukemiaNet (ELN) criteria for response to second line therapy (i.e. "Failure" category in table 6, below), despite recommended optimization of therapy

Table 4. ELN criteria for response in 2nd line therapy of CML.

	Optimal	Warning	Failure
3 months	BCR-ABL < or	BCR-ABL >10% or	Ph+ >95%.
	=10% and/or	Ph+ 65-95%	
6 months	BCR-ABL < or	Ph+ 35-65%	BCR-ABL >10%
	=10% and/or Ph+		and/or Ph+ >65%
	<35% (i.e. MCyR)		and/or new
			mutations
12 months	BCR-ABL <1%	BCR-ABL 1-10%	BCR-ABL >10%
	and/or Ph+ 0 (i.e.	and/or Ph+ 1-35%	and/or Ph+ >35%
	CCyR)		and/or new
			mutations

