14.0 ABBREVIATION LIST	

1.0 OBJECTIVES

Primary:

To assess the response rate within 24 weeks in patients in chronic phase receiving bosutinib with the starting dose of 300 mg per day, with potential escalation to 400mg, 500 mg and 600mg per day.

Response is defined as follows:

- 1. For patients who do not currently have a partial cytogenetic response (PCyR), achievement of major cytogenetic response (MCyR) is considered a response.
- 2. For patients who are currently in PCyR, achievement of complete cytogenetic response (CCyR), CCyR is considered a response.

Secondary:

- Safety of dosing schedule.
- Frequency of treatment interruptions and dose reductions.
- Determine the rate of BCR-ABL/ABL <10% at 3 months and <1% at 6 months, reported
 on the international scale, and the rate of complete cytogenetic response (CCyR) at 6
 months after the start of treatment.
- Determine the cumulative rate of CCyR.
- Determine the rate of major molecular response, MR4, MR4.5 and complete molecular response.
- Determine long-term outcomes, including progression-free survival, event-free survival, and overall survival.
- Investigate the correlation between ABL kinase domain mutations, if present at the time of enrollment, with outcome.

 Determine the rate of development and type of ABL kinase domain mutations during therapy with bosutinib.

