6.0 TREATMENT PLAN

Bosutinib will be commenced at 300mg/d. Subsequent dose changes may be made in the event of inadequate response or toxicity, according to the dose levels in table 2.

Table 2. Bosutinib dose levels

Dose level	Bosutinib (mg)
+3	600
+2	500
+1	400
Starting dose	300
-1	200
-2	100

6.1 Management of bosutinib dosing.

Patients may have their dose increased by one dose level, at the 1, 3, 6 and 12 month assessments, if they do not achieve or subsequently lose the following therapeutic milestones:

- i) month 1, complete hematologic response;
- ii) month 3, BCR-ABL1 transcripts < or = 10% and/or Ph + metaphases < or = 35%;

- iii) month 6 BCR-ABL1 transcripts < or = 1% and/or Ph + metaphases 0%);
- iv) month 12, BCR-ABL1 transcripts <0.1%. All BCR-ABL targets refer to the international scale.

AND

They do not currently have grade >/= 3 hematologic or grade >/=2 non-hematologic toxicity.

- **6.1.1** Patients who had their dose reduced for any reason may have the dose re-escalated after at least 28 days at the lower dose provided they do not currently have grade >/= 3 hematologic or grade >/=2 non-hematologic toxicity.
- **6.1.2** At least 28 days should have elapsed from a prior dose escalation before a new dose escalation can be implemented, and the patient should not currently have grade >/= 3 hematologic or grade >/=2 non-hematologic toxicity. The highest dose level to be used in this study is 600 mg daily.
- **6.1.3** Dose escalations outside the above timepoints may be initiated by the treating physician if deemed to be in the best interests of the patient, with the approval of the PI.

6.2 Bosutinib dose reductions:

General guidelines include the following:

a) Non-Hematologic Toxicity

- **Grade 2:** Patients with persistent grade 2 toxicity that is unresponsive to appropriate therapy, may have treatment held until the toxicity has resolved to grade < or =1. Bosutinib may then be resumed at the same dose the patient was receiving at the time treatment was interrupted. If the grade 2 toxicity recurs, bosutinib may be held until the toxicity has resolved to grade 1. Treatment may then be resumed with a one dose level reduction.
- Grade 3-4: If a patient experiences Grade 3-4 toxicity that is related to bosutinib,
 therapy must be withheld until the toxicity has resolved to Grade < or = 1. Bosutinib

may then be resumed with a one dose level reduction.

b) Hematologic Toxicity

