11.0 STATISTICAL CONSIDERATIONS

This is a single-arm open-label phase II study to assess the response rate achieved with bosutinib therapy in patients with chronic phase CML who have experienced resistance or intolerance to frontline TKI therapy. Patients will receive an escalating schedule of bosutinib with the starting dose of 400 mg per day. The primary endpoint is response rate, as defined in section 1.0, within the first 6 months therapy. The Simon's optimal two-stage design will be used for interim futility monitoring. The null hypothesis is that the response rate is 20% and our target rate under the alternative hypothesis is 35%. Under the design, we will enroll 20 patients in the first stage. If 4 or fewer patients achieve the primary endpoint, enrollment of future patients will be halted. If 5 or more out of the first 20 patients have met the primary endpoint, accrual will continue until a total of 42 patients are enrolled. If 12 or more out of these 42 patients achieve the primary endpoint, the treatment will be considered efficacious and is worth further investigation. Under this Simon's optimal two-stage design, the type I error is 0.101, the power is 79.8%, the probability of early

termination is 0.63 if the true hematologic remission rate is 20% and the expected sample size is 28.2 patients. After the first stage, if <5 responders are observed in the first 20 patients, we will temporarily suspend the accrual until a sufficient number of responders (i.e., >/=5) is reached.

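### Table 4's Optimal and Failure categories overlap, so a primary-endpoint responder with discordant results or a new mutation can also meet removal criterion 5 in Section 10

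*Combined protocol and SAP*

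**What the plan says.** Section 10 item 5 gives as a reason for removal "Failure to respond at 3, 6, 12 months according to European LeukemiaNet (ELN) criteria for response to second line therapy". It points to the Failure category and adds the condition "despite recommended optimization of therapy". Section 10 does not say what that optimization is. Item 5 refers to table 6 for the categories, but they stand in Table 4, directly below it.

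The two Table 4 rows that matter here, in short form:

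| | Optimal | Warning | Failure |
|---|---|---|---|
| 6 months | BCR-ABL ≤10% and/or Ph+ <35% (labelled MCyR) | Ph+ 35-65% | BCR-ABL >10% and/or Ph+ >65% and/or new mutations |
| 12 months | BCR-ABL <1% and/or Ph+ 0 (labelled CCyR) | BCR-ABL 1-10% and/or Ph+ 1-35% | BCR-ABL >10% and/or Ph+ >35% and/or new mutations |

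No rule says which measurement prevails when they disagree.

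The primary endpoint is purely cytogenetic. Section 1.0 states: "For patients who do not currently have a partial cytogenetic response (PCyR), achievement of major cytogenetic response (MCyR) is considered a response". For the other group it states: "For patients who are currently in PCyR, achievement of complete cytogenetic response (CCyR), CCyR is considered a response". Section 8.2 gives "Major cytogenetic response, 0%-35" (per cent Ph+), with no condition on transcript level or mutation.

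Section 8.4 includes "treatment discontinuation for any reason" among the failure-free survival (FFS) events.

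**The concern.** A rule that can end a patient's participation should put each result in one category. Here two people reading the same 6-month results correctly could reach opposite answers, and one of those answers is a ground for removal. The response definition looks only at Ph+, while Failure can be met on transcripts or a mutation alone. The conflict therefore reaches patients whom the trial counts as successes.

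A responder removed in this way is a primary-endpoint success and, through discontinuation, an FFS event. Event-free survival in Section 8.4 counts only events during study treatment, so it too would lose later follow-up. Later molecular and cytogenetic response rates could lose observations as well. Those results would then depend partly on which cell was read.

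**Working it through.** **1. The plan's own figures.** Section 11.0 states: "The null hypothesis is that the response rate is 20% and our target rate under the alternative hypothesis is 35" (per cent). Stage 1 has 20 patients and stops at 4 or fewer responders; the final rule is 12 or more of 42.

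- Probability of early termination: P(X1 ≤ 4), X1 ~ Bin(20, 0.20) = 0.6296 (stated 0.63).
- Type I error: sum over x = 5 to 20 of P(X1 = x) × P(X2 ≥ 12 − x), X2 ~ Bin(22, 0.20) = 0.1009 (stated 0.101).
- Power: the same sum at 0.35 = 0.7975 (stated 79.8%).
- Expected size: 20 + (1 − 0.6296) × 22 = 28.15 (stated 28.2).

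The design reproduces, apart from the last digit of the expected size.

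**2. Two patients at month 6.** Cycle 6 day 28 is 6 × 28 = 168 days = 24 weeks, so the scheduled visit for the 6-month row falls at the end of the primary-endpoint window.

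- Ph+ 6/20 = 30%, BCR-ABL 12%, no new mutation. Optimal through Ph+ <35%; Failure through BCR-ABL >10%. If the patient entered without PCyR, also a responder. If the patient entered in PCyR, not a responder; that group needs Ph+ 0.
- Ph+ 30%, BCR-ABL 8%, new mutation. Optimal on both limbs; Failure through the mutation.

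**3. All combinations at month 6.** Cross BCR-ABL (≤10%, >10%) with Ph+ (0, 1-34, 35, 36-65, 66-95, >95%) and new mutation (no, yes): 2 × 6 × 2 = 24 cells, of which 2 × 3 × 2 = 12 are MCyR under 8.2.

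| Reading of the connectors | Optimal and Failure (of 24) | MCyR and Failure (of 12) | MCyR, Optimal and Failure |
|---|---|---|---|
| Inclusive or throughout | 12 | 9 | 7 |
| Optimal needs both limbs; Failure inclusive | 2 | 9 | 2 |
| Optimal inclusive; Failure needs both levels, or a new mutation | 8 | 6 | 5 |
| Every Failure connector read as and | 0 | 0 | 0 |

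Of these readings only the last removes the overlap, and the text does not say it. The entries count logical combinations, not patients. MCyR with BCR-ABL ≤10% and no new mutation is never Failure on any reading.

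**4. Month 12.** BCR-ABL (<1, 1-10, >10%) × Ph+ (0, 1-35, >35%) × mutation gives 3 × 3 × 2 = 18 cells. Seven are both Optimal and Failure: Ph+ 0 with BCR-ABL >10%, with or without a mutation (2); BCR-ABL <1% with Ph+ >35%, with or without a mutation (2); and the remaining Optimal cells with a new mutation (3).

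**5. From Failure to item 5.** Failure alone is not enough; therapy must already have been optimized. The nearest text is the escalation rule in 6.1, whose month 3 milestone reads "month 3, BCR-ABL1 transcripts < or = 10% and/or Ph + metaphases < or = 35" (per cent). It uses the same connector, so whether a discordant patient missed it is itself unclear. At month 6 the milestones in 6.1 are BCR-ABL ≤1% and/or Ph+ 0. The first patient in step 2 misses both and may have the dose raised if toxicity allows, while Table 4 calls the same result Optimal and Failure. For a patient already escalated at month 1 or 3, the condition can be read as met.

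**6. The 35% boundary.** 7/20 = 35% is an attainable count. It is MCyR in 8.2 and within the month 3 milestone in 6.1. Table 4 equates MCyR with <35% and lists 35% under Warning at 6 months.

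**7. Size for FFS.** One removal that would not otherwise be an event moves the FFS proportion by at most 1/42 = 2.4 percentage points. The documents give no discordance rate. If 5-10% of 42 patients were discordant or had a new mutation while in MCyR (an assumption), that is 2 to 4 patients, or 2/42 = 4.8 to 4/42 = 9.5 points as an upper bound.

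**The case against.** The strongest reply is that item 5 is conditional. A patient newly in MCyR with BCR-ABL 12% may first have the dose raised under 6.1, and Section 10 lists criteria without saying that removal is automatic. This stands: a reader might infer that reaching MCyR at 6 months in itself satisfies the removal rule, and the documents do not support that. The condition does not cure the defect, because it is undefined and can already be met by month 6.

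Second, few patients may be involved. Only discordant or new-mutation patients are affected, MCyR is the endpoint only for those not in PCyR at entry, and after screening Section 7 calls for sequencing only as clinically indicated. This stands, and it is why the range above is a ceiling.

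Third, a reader might infer that the efficacy conclusion is at risk. It is not: nothing in Sections 1.0 or 11.0 withdraws a response reached within 24 weeks because the patient is later removed. FFS is also not among the Section 1.0 objectives; it appears in 8.4 and the analysis plan. That response follow-up would stop on removal is likewise an inference, since the documents do not say so.

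Two further readings fail. At 12 months a new mutation does not put every MCyR patient in both categories: with Ph+ 1-35% and BCR-ABL ≥1% the patient is not Optimal. Nor do the documents support divergence between sites, as they name only one centre; the ambiguity is between readers. The wrong table number is clerical.

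**Conclusion.** The point holds in a limited form. Table 4 read as written contradicts itself at 6 and 12 months, and through item 5 a primary-endpoint responder can also meet a removal criterion. This requires discordant results or a new mutation, therapy already optimized and, where the response is MCyR short of CCyR, entry without PCyR.

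The 12-of-42 rule, type I error and power are unchanged, on the footing that a response counts once reached within 24 weeks. The exposure is FFS, by up to 2.4 percentage points per removed patient, and later secondary endpoints. The 4.8 to 9.5 point range rests wholly on the assumed 5-10% rate, and on every such patient being already optimized, removed and otherwise free of an FFS event. This should be corrected, but it does not put the main result in doubt.

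**What to change.** Reconcile Table 4 and item 5 with Sections 1.0, 6.1 and 8.2:

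- Reword the three columns so that each combination of transcript level, Ph+ and mutation status falls in exactly one category, and state how discordant results are classified.
- Align the 35% boundary with 8.2, so that the MCyR label means the same thing in both places.
- State what counts as recommended optimization for item 5.
- Change the reference in item 5 from table 6 to Table 4.
- For any item 5 removal, record the category and the measurement behind it, so that FFS can be reported with removals of patients in MCyR shown separately.

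Which clinical criterion governs is for the sponsor to decide. The cost is a wording amendment and one case report form field; no extra tests or patients are needed.

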11.0 STATISTICAL CONSIDERATIONS

This is a single-arm open-label phase II study to assess the response rate achieved with bosutinib therapy in patients with chronic phase CML who have experienced resistance or intolerance to frontline TKI therapy. Patients will receive an escalating schedule of bosutinib with the starting dose of 400 mg per day. The primary endpoint is response rate, as defined in section 1.0, within the first 6 months therapy. The Simon's optimal two-stage design will be used for interim futility monitoring. The null hypothesis is that the response rate is 20% and our target rate under the alternative hypothesis is 35%. Under the design, we will enroll 20 patients in the first stage. If 4 or fewer patients achieve the primary endpoint, enrollment of future patients will be halted. If 5 or more out of the first 20 patients have met the primary endpoint, accrual will continue until a total of 42 patients are enrolled. If 12 or more out of these 42 patients achieve the primary endpoint, the treatment will be considered efficacious and is worth further investigation. Under this Simon's optimal two-stage design, the type I error is 0.101, the power is 79.8%, the probability of early

termination is 0.63 if the true hematologic remission rate is 20% and the expected sample size is 28.2 patients. After the first stage, if <5 responders are observed in the first 20 patients, we will temporarily suspend the accrual until a sufficient number of responders (i.e., >/=5) is reached.

We will also monitor treatment emergent toxicities using a Bayesian design by Thall, Simon and Estey, starting from the 6th patient and then in cohort size of 6. For monitoring purposes, toxicity is defined as the occurrence of grade 3-4 hematologic or nonhematologic toxicity leading to treatment discontinuation and the associated toxicity stopping rule is to stop the trial if Prob{p(TOX) > 0.35| data} > 0.90, where p(TOX) is the toxicity rate and a beta(0.7, 1.3) distribution was assumed for the prior. That is, if at any time during the trial we determine that there is more than 90% chance that the toxicity rate is more than 35%, we will stop the trial due to safety concern. The corresponding stopping boundaries are shown in Table 1 below and the operating characteristics of the toxicity monitoring are illustrated in Table 2. Multc Lean Desktop (v2.1.0) (https://biostatistics.mdanderson.org/SoftwareDownload/) was used for generating the stopping boundaries and the OC table. Toxicities will be monitored continuously over the two year duration of the study.

Table 5. Toxicity stopping boundaries in cohort size of 6.

Number of patients	Stop the trial if there are			
	this many patients having			
	toxicity			
6	4-6			
12	7-12			
18	10-18			
24	12-24			
30	15-30			
36	17-36			

Always stop with this many patients

Table 6: Operating characteristics for toxicity monitoring.

True Toxicity	Early	Average	25th, 75th
Rate	Stopping	number of	percentile
	Probability	patients	
		treated	
0.25	0.050	40.4	42, 42
0.30	0.112	38.6	42, 42
0.35	0.227	35.6	42, 42
0.40	0.400	31.2	18, 42
0.50	0.789	20.6	6, 36
0.60	0.974	12.4	6, 18

Analysis Plan:

The response rate will be estimated along with the 95% credible interval. Data from all subjects who receive any study drug will be included in the safety analyses. The severity of the toxicities will be graded according to the NCI CTCAE v4.0 whenever possible. We will follow standard reporting guidelines for adverse events. Safety data will be summarized by AE category, severity and frequency. The Frequency of treatment interruptions and dose reductions will be summarized. The rates of major molecular response, MR4, MR4.5 and complete molecular response will be estimated along with the exact 95% confidence intervals. Similarly, the rates of BCR-ABL/ABL <10% at 3 months and BCR-ABL/ABL <1% at 6 months since treatment start, on the international scale, will be estimated along with the exact 95% confidence intervals. Kaplan-Meier method will be used to assess the overall survival (OS), failure-free survival (FFS), failure-free survival (FFS) and transformation-free survival (TFS). Cox proportional hazards regression models will be fit to assess the association between patient characteristics including ABL kinase domain mutation status and each survival outcome. In addition, the change of ABL kinase domain mutation status

over time will be summarized and its association with survival outcomes will be analyzed through landmark analyses.

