2.0 STUDY DESIGN

The study is an open-label phase II trial in patients with CML in chronic phase who have experienced resistance or intolerance to frontline TKI therapy. The starting dose of bosutinib is 300 mg per day. Patients will have the opportunity to dose escalate to 400mg, 500mg and subsequently to 600mg if therapeutic targets are not met and toxicity does not preclude such dose escalation.

Toxicity will be monitored continuously, throughout the duration of the study.

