3.5. Rationale for the starting dose of 300 mg per day of bosutinib

The first studies in 2nd line and first line therapy used 500mg/d. In both studies, a substantial number of patients reported toxicities. The incidence of treatment emergent AEs (TEAEs)

overall as well as unique TEAEs were lower following dose reduction from 500 mg to 400 mg, while the efficacy of bosutinib in patients who received dose reductions to 400 mg remained favorable.

Therefore, it was concluded that a starting dose of 400 mg daily would be used in this phase II study in patients post frontline TKI failure, with potential escalation to 500 mg daily and subsequently to 600mg daily, if therapeutic targets at pre-specified timepoints are not met and toxicity is within acceptable limits. By starting at a lower dose and dose-escalating as tolerated/necessary, we will minimize dose interruptions, which may compromise efficacy. We hypothesize that such a dosing strategy will result in better tolerability and similar, if not superior, efficacy as a starting dose of 500 mg daily.

Recently, results of the BFORE study were published, demonstrating favorable efficacy (higher rate of MMR at 12 months with a dose of 400mg bosutinib than when starting with 500mg in the BELA study), confirming the above hypothesis. However, there was still a significant incidence of grade 3-4 toxicity and dose interruptions/reductions, which may have a greater impact on efficacy than receiving a lower, consistent dosing schedule. Additionally, in the first 8 patients treated on this study, we have had 3 patients with grade 3-4 toxicity (elevated LFTs in 2 patients and diarrhea in 1 patient). Therefore, we subsequently amended the study to commence dosing at 300mg per day, with the option to escalate doses if therapeutic targets are not met during treatment.

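### Section 11.0 describes a 400 mg start while Sections 1.0, 2.0 and 6.0 name 300 mg, and as written the primary test pools patients treated before the change, with no response rate planned by starting dose

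*Combined protocol and SAP*

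**What the plan says.** The opening of Section 11.0 describes the regimen under test: "Patients will receive an escalating schedule of bosutinib with the starting dose of 400 mg per day". Three other current sections name a different start:

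- Section 1.0, primary objective: "To assess the response rate within 24 weeks in patients in chronic phase receiving bosutinib with the starting dose of 300 mg per day".
- Section 2.0: "The starting dose of bosutinib is 300 mg per day".
- Section 6.0: "Bosutinib will be commenced at 300mg/d".

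Section 3.5 gives the history. First "it was concluded that a starting dose of 400 mg daily would be used in this phase II study"; then "in the first 8 patients treated on this study, we have had 3 patients with grade 3-4 toxicity"; and for that and other reasons "we subsequently amended the study to commence dosing at 300mg per day". The 400 mg sentence in Section 3.5 is narrative about the earlier plan and is not itself part of the contradiction.

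The decision rules in Section 11.0 count patients by order of enrolment. Accrual continues "If 5 or more out of the first 20 patients have met the primary endpoint", and success needs at least 12 responders among 42. Section 4.0 also gives 42 enrolled. None of these sentences mentions starting dose, and none excludes, replaces or restarts the count for patients already treated. The Analysis Plan in Section 11.0 provides one response rate with one 95% interval. Its regression models concern survival outcomes only and do not name starting dose.

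**The concern.** The section that defines the primary test and the section that states the primary objective describe different starting doses. Because the change came after patients had been treated, correcting one number does not settle the matter. The plan should also say how the earlier patients enter a test whose objective names one starting dose.

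Two things are at stake. First, the stated error rates describe the schedule in the objective only if response does not depend on starting dose, or if every counted patient started at that dose. Second, with one pooled rate and no split, a reader of the final report cannot see the response rate in patients who received the schedule named in the objective.

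**Working it through.** **Inputs.** From Section 11.0: null rate 0.20, target rate 0.35, stage 1 of 20 patients, stop at 4 or fewer responders, total 42, success at 12 or more. From Section 3.5: at least 8 patients treated before the amendment. The documents give no response rate by starting dose, so every gap below is an assumption.

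**1. Reproduce the plan's own figures.** With a common rate p:

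P(success) = Σ over x = 5 to 20 of Bin(x; 20, p) × P[Bin(22, p) ≥ max(0, 12 − x)]

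| Quantity | Stated | Recomputed |
|---|---|---|
| Type I error (p = 0.20) | 0.101 | 0.1009 |
| Power (p = 0.35) | 79.8% | 0.7975 |
| Early stop, P[Bin(20, 0.20) ≤ 4] | 0.63 | 0.630 |
| Expected N, 20 + (1 − 0.6296) × 22 | 28.2 | 28.15 |

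The design figures are correct. They do not depend on the dose label, but they do assume one response rate for all 42 patients.

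**2. Let the earlier patients have a different rate.** Take exactly 8 earlier patients with rate q. They were the first 8 treated, so all fall in stage 1. The other 34 have rate p. The stage 1 count is then Bin(8, q) + Bin(12, p), stage 2 is Bin(22, p), and the rules are unchanged. By share of patients, the 8 are 8/20 = 40% of the futility look and 8/42 = 19% of the final test.

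| Rate p in the 34 | Rate q in the 8 | P(early stop) | P(success) |
|---|---|---|---|
| 0.20 | 0.15 | 0.715 | 0.071 |
| 0.20 | 0.20 | 0.630 | 0.101 |
| 0.20 | 0.25 | 0.542 | 0.136 |
| 0.35 | 0.30 | 0.159 | 0.749 |
| 0.35 | 0.35 | 0.118 | 0.798 |
| 0.35 | 0.40 | 0.086 | 0.839 |

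Larger assumed gaps move these figures further.

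**3. Change the target to the average over all 42.** Fix the mean at 20%, so p = (42 × 0.20 − 8q)/34 = (8.4 − 8q)/34. With q = 0.15, p = 0.212 and type I error is 0.094. With q = 0.25, p = 0.188 and it is 0.106. With q = 0.35, p = 0.165 and it is 0.109. On this reading pooling hardly matters, but the average over a mix of starting doses is not the quantity named in Section 1.0.

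**4. Precision of a split (exact 95% intervals).** 12/42: 15.7% to 44.6%. 10/34: 15.1% to 47.5%. 2/8: 3.2% to 65.1%. The larger subgroup loses little precision. The smaller one cannot support a comparison of doses.

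**The case against.** The best defence is that only one descriptive sentence in Section 11.0 carries 400 mg. The hypotheses, stage rules and success rule name no dose, and the endpoint is defined by reference to Section 1.0. Section 3.5 lets a reader see how the difference arose. The literal counting rule is also clear: everyone enrolled counts. All of this stands. It means that no design figure is wrong and that no boundary has to change.

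It is also fair that the harm rests on an assumed gap. A 5-point gap in 8 of 42 patients moves the overall mean by 8 × 5/42 = 0.95 points. The direction is open. Section 3.4 reports that a lower dose did not compromise efficacy, although for 400 against 500 mg in frontline patients, so the evidence is indirect. Section 3.5 suggests that interruptions may matter more than a lower, steady dose. Section 6.1 allows escalation at months 1 and 3, before the 24-week endpoint, which may narrow any gap. These points limit the size of the problem. They do not remove the contradiction, and they do not supply the missing result by starting dose.

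A reader might infer more than the documents support:

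- **That Section 11.0 tests a 400 mg hypothesis.** It does not; the hypothesis sentence names no dose.
- **That the type I error is inflated.** Nothing in the documents shows a gap, or its sign.
- **That the plan drops the earlier patients and so tests only 34.** No passage says this, and the number treated before the amendment is not given; Section 3.5 supports only at least 8. That they started at 400 mg is itself an inference from that section.

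**Conclusion.** The concern holds in this form: current sections contradict each other on the starting dose, and as written the primary test pools patients treated before and after the change, with a single response rate planned for an objective that names one starting dose. No sentence says that pooling was intended.

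The contradiction and the absence of a split are certain; the numerical effect is not. With exactly 8 earlier patients and an assumed 5-point gap either way, type I error for the schedule in the objective is 0.071 to 0.136 against the stated 0.101, and power is 0.749 to 0.839 against 79.8%. With no gap nothing changes, and for the all-enrolled average type I error stays at 0.094 to 0.109. This should be fixed because the correction is cheap and lets the trial answer the question it poses. It does not show that the design is invalid, and it implies no view on which starting dose is right.

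**What to change.** 1. Reconcile the starting dose across Sections 1.0, 2.0, 6.0 and 11.0.
2. State in Section 11.0 that all enrolled patients count in the 20 and in the 42, as the text literally reads, with boundaries unchanged. Add that the stated error rates assume a common response rate across starting doses.
3. Report the primary response rate and its interval by starting dose, descriptively, beside the all-enrolled result.

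The cost is a few sentences and one table, with no extra patients. The table will show the rate for the schedule in the objective, but the earlier subgroup will probably be too small to compare doses.

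If the sponsor prefers to exclude the earlier patients, the boundary, type I error and power must be recomputed from the actual number excluded. The result is sensitive to that number: keeping the look at 5 or more of 20 counted patients and setting success at 10 or more, type I error is 0.113 with 34 counted patients, 0.085 with 32 and 0.060 with 30. The plan should then record that the change was made after patients had been treated, and whether their responses were known.
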